## 16.2. Statistical Analysis

The primary study analysis time point for all relevant outcomes is 12 weeks post randomization. The original analysis plan called for ANCOVA, controlling for baseline value of each relevant outcome in addition to the following baseline covariates: sex, age at baseline, race/ethnicity, health literacy level (indicator of limited literacy as defined by the Newest Vital Sign instrument), and an indicator of monotherapy at baseline (vs. untreated; this variable will serve as a stratification factor for randomization). These variables are deemed clinically relevant and important covariates; thus, all analyses will plan for adjustment for these covariates of interest (regardless of statistical significance in the current dataset) in predicting outcome in the present study. However, to better align with the analytic strategies of the QUARTET Australia study, and to make most efficient use of all follow-up data (both six-week and 12-week data), primary analyses will involve a linear mixed model with fixed study arm and baseline outcome value effects and a random participant effect to account for within-participant correlation. We plan to conduct both unadjusted (for potential covariates mentioned above) and adjusted analyses. The updated details of these analyses are reserved for the statistical analysis plan. The basic analytic model will be as follows for each outcome ( $Y$ ) for participant  $i$  ( $i=1\dots N$ ) at visit  $j$  ( $j=1,2$ ; corresponding to Week 6 and Week 12):

$$Y_{ij} = \beta_0 + \beta_1 I(LDQT) + B_2(Y_{0i}) + B_3 visit + B_4(visit \times study\ arm) + b_i + e_{ij}$$

Under the assumption that error terms  $e_{ij} \sim N(0, \sigma^2)$  is the random error term,  $b_i \sim N(0, \sigma_b^2)$  is the participant-level random effect. If visit-by-study arm ( $B_4$ ) is insignificant at the 5% level, we will remove that term from the model, and subsequently, we will further examine for an overall main effect for visit ( $B_3$ ). If insignificant, we will also remove that effect from the model and evaluate intervention effect via the primary hypothesis test of interest:

$$H_0: \beta_1 = 0 \text{ vs. } H_1: \beta_1 \neq 0$$

for each outcome. However, if the visit-by-study arm interaction term or the visit term alone is significant, we will plan to evaluate the 12-week contrast via model-estimated least squared means as our primary analyses. All between-arm differences at both six- and 12-week time points will be reported as model-based estimates, corresponding 95% confidence limits, and p-value of the corresponding hypothesis test.

Secondary analyses will utilize data from all time points via (generalized) linear mixed modeling (GLMM) methods with the following specifications: identity, logit, or log link for continuous, binary, or count outcomes, respectively; fixed arm, visit, visit-by-arm interaction, and aforementioned covariates; and random participant effect. For secondary analyses, the model adjusted Wald type III tests for fixed effects will first evaluate significance of a visit-by-arm interaction at the relaxed 10% level of significance. If insignificant at the 10% level, then this interaction term will be removed and the model Wald type III test for fixed arm effect will evaluate the overall intervention effect in this longitudinal model at the 10% level (since these analyses are exploratory and secondary).

Safety outcomes will be treated similarly: adverse event rates and relevant outcomes previous listed will be tabulated overall and by arm. Chi-squared tests or exact methods will evaluate the differences across arms in event rates at the participant level. For outcomes such as relevant side effects that may occur more than once in any participant, descriptive statistics or GLMMs as specified above will be examined, and continuous laboratory safety assessments will also be analyzed as specified above (GLMMs, as appropriate).

Procedures for control and handling of specimens are described within the Laboratory Procedures document.

## **17. PROVISIONS TO MONITOR THE DATA TO ENSURE THE SAFETY OF PARTICIPANTS**

The DSMP documents the provisions to monitor the data and ensure safety of all study participants. Briefly, (1) we have convened an independent DSMB consisting of five members with diverse backgrounds and fields of expertise, including an expert in research methodology and ABPM, a biostatistician, a clinician-scientist with expertise in hypertension combination treatment trials and prevention of heart and kidney disease, an ethicist, and a patient representative; (2) the DSMB will meet at minimum every six months to review safety and essential study data; (3) we will employ centralized monitoring approaches as mentioned above to monitor data quality and safety; (4) we will program an email alert to study staff in the event of an SAE; (5) we plan for targeted on-site monitoring by an external clinical research associate; (6) and we will adhere to regulatory requirements for expedited AE / SAE reporting.

## **18. PROVISIONS TO PROTECT THE PRIVACY INTERESTS OF PARTICIPANTS**

Information regarding patient privacy relevant to data and specimens is described within this protocol in section Data and Specimen Banking. All study related procedures and visits will occur at Access Community Health Network clinics which complies with federal regulations for patient privacy. All study-related visits will be completed in a designated enclosed study-room whereby only the study participant and study team (e.g. research coordinator and/or research nurse) will be present. The study room is in the back end of the health center far removed from clinical rooms, nurse stations, and reception/waiting room area whereby study participants may feel at ease to discuss matters as it relates to their participation in the research study.

## **19. COMPENSATION FOR RESEARCH-RELATED INJURY**

This study is investigator-initiated. If participants become ill or are injured as a result of this study (medications, devices or procedures), they are directed to seek medical treatment through their doctor or treatment center of choice and to promptly tell the study doctor about any illness or injury. The researchers and clinical staff will not pay for medical care required because of a bad outcome resulting from participation in this research study. This does not keep participants from seeking to be paid back for care required because of a bad outcome.

## **20. ECONOMIC BURDEN TO PARTICIPANTS**

We do not anticipate that patients will experience economic burdens related to participation in this study. Evaluation of hypertension will be performed according to clinical practice guidelines. Twelve-week treatment will be provided at no cost to participants. Participants will be reimbursed for their time and travel costs for study related visits.

## **21. CONSENT PROCESS**

Participation will require informed consent from all participants. The study coordinator will consent participants at Access Community Health Network clinics or through a telehealth visit. Consent will be taken by the study coordinator and the research nurse will be available to consult during the consent process. Ample time will be devoted to the consent process according to participant request. Participants will be allowed time to consider the trial and ask questions and will be reminded they are free to leave the trial at any time. Prior to randomization, we will confirm participant consent and understanding of the trial. At each study follow-up visit, the consent will be confirmed.

- If conducted in person, both the participant and witness will sign and date two copies of the consent form if the participant agrees to the study procedures. A hard copy will be kept in the participant's file, housed at the health center where the study is being conducted (in a locked file cabinet in a locked closet). The participant will be provided with the other copy to take home.
- If conducted via a telehealth visit, the participant will have two options on how to complete consent form:
  - A. The participant will receive an electronic version of consent form (eConsent) as an automated survey sent from a 21 CFR, Part 11 compliant instance of REDCap. The participant will electronically sign and date the consent form, which will be stored in REDCap. The witness will electronically sign and date the consent form after the participant has completed the REDCap eConsent survey. A hard copy will be kept in the participant's file, housed at the health center where the study is being conducted (in a locked file cabinet in a locked closet). The participant will be sent a link to the executed electronic consent form.

- B. The participant will receive a hard copy of the consent form sent via regular mail or will print out a copy that is emailed to them through the patient's ACCESS MyChart account within Epic. The participant will provide a wet signature, will date the consent form, and will upload an image of the last page with their signature to their ACCESS MyChart account. A copy of the signed signature page of the consent will be saved in the patient's electronic health record. The witness will be able to print the signed form and provide a wet signature and date. A hard copy will be kept in the participant's file, housed at the health center where the study is being conducted (in a locked file cabinet in a locked closet).

## **22. PROTECTED HEALTH INFORMATION (PHI AND HIPAA)**

This study involves collection and use of Protected Health Information. All participants will be identified by a unique study ID. Access to the full study database with identifying information (names, medical record numbers, dates, ages, email and telephone) will be restricted to authorized study personnel. Data collection will be secure, and these data will not be used for any other purpose than to contact the study participant during their participation in the trial and to disseminate results. Data shared from this study will be completely de-identified.

The informed consent form for this study includes HIPAA authorization.

## **23. NON-ENGLISH-SPEAKING PARTICIPANTS**

We anticipate enrolling Spanish speaking participants in this study. Prior enrollment of any primarily Spanish speaking participants, all participant-facing study documents will be translated and back-translated for quality assurance, reviewed and approved by the IRB. All study drug will include labelling in both English and Spanish. Informed consent will be completed in either English or Spanish, according to participant preference.

## **25. MULTI-SITE OR COLLABORATIVE RESEARCH:**

Northwestern investigators will collaborate with the research team at Washington University in St. Louis and Access Community Health Network. Study procedures will occur at the Access Community Health Network, where informed consent will be sought and study procedures will be conducted. The Northwestern IRB will serve as the IRB of record, and no activities will occur at Washington University in St. Louis until the SMART IRB LOA reliance agreement has been fully executed and appropriate local regulatory processes are followed and completed. The project is federally funded. The IRB approved the initial protocol before the Cooperative Research Requirement effective date. A single IRB is not required but is permissible.

Northwestern University has served as the prime institution since the study start in 2018. As of January 2022, the prime institution will be Washington University in St. Louis based on the institutional change by the contact mPI, [name]. Enrollment will be completed in May 2022. The Access Community Health Network has agreed for Northwestern to serve as the IRB of record in accordance with their local policies.

1. INTRODUCTION

This document outlines the proposed analyses for the QUARTET USA phase II clinical trial, which aims to compare clinical and safety outcomes for adult participants with elevated blood pressure (BP) at baseline who receive treatment with ultra-low-dose quadruple-combination therapy (LDQT) to those outcomes in participants given standard dose monotherapy at 12 weeks. Thus, we plan to conduct a two-arm, double-blind randomized controlled trial with equal allocation (1:1) in adults with uncontrolled blood pressure who are eligible for monotherapy. The purpose of this document is to provide detail regarding the statistical analysis plan (SAP) for this study.

Study Aims

The overarching study aims are as follows:

Aim 1: To investigate whether initiating treatment with ultra-low-dose quadruple-combination therapy ("LDQT") including candesartan 2mg, amlodipine 1.25mg, indapamide 0.625mg, and bisoprolol 2.5mg will lower office blood pressure at 12 weeks more effectively, and with no increase in side effects, compared to initiating standard dose monotherapy (candesartan 8mg) in adults with elevated blood pressure who are eligible for monotherapy based on the 2017 AHA/ACC guideline.

We hypothesize that initiating treatment with LDQT will lower office blood pressure at 12 weeks more effectively, and with no increase in side effects, compared to initiating standard dose monotherapy in adults with elevated blood pressure who are eligible for monotherapy.

Aim 2: To investigate whether initiating treatment with LDQT will lower mean 24-hour ambulatory blood pressure at 12 weeks more effectively, and with no increase in side effects, compared to initiating standard dose monotherapy in adults with elevated blood pressure who are eligible for monotherapy.

We hypothesize that initiating treatment with LDQT will lower mean 24-hour ambulatory blood pressure at 12 weeks more effectively, and with no increase in side effects, compared to initiating standard dose monotherapy in adults with elevated blood pressure who are eligible for monotherapy.

Exploratory Aim 1: Assess heterogeneity of treatment effect by hypothesized moderators (age, sex, race/ethnicity, and health literacy level).

We hypothesize that the treatment effect of LDQT will be greater in participants with limited health literacy than those with adequate health literacy. We also hypothesize that treatment effect of LDQT will differ by age, sex, and race/ethnicity subgroups.

Exploratory Aim 2: To evaluate acceptability, preferences, and lessons for implementation of LDQT among patients and clinicians using mixed methods.

We hypothesize that patients and clinicians will prefer LDQT more than standard dose monotherapy for initial blood pressure lowering therapy; we further hypothesize that LDQT will be simpler and easier for both patients and clinicians than standard dose monotherapy for initial blood pressure lowering therapy, including patients with low health literacy.

This SAP will focus on the details of analyses for Aims 1, 2, and part of exploratory Aim 1 (pertaining to age, sex, and race/ethnicity as potential moderators); we reserve details of the exploration of health literacy and implementation analyses (exploratory Aim 2) for a separate document.

Study time points include baseline assessment (completed over approximately two days), a six-week follow-up time point, and a 12-week follow-up time point (also completed over approximately two days).

2. STUDY OUTCOMES

In the sections below, we include the relevant specific field names for variables within the study database as of the time of SAP creation. These are indicated by the [brackets].

Primary Outcome

Primary efficacy outcome is **mean change (from baseline) in automated office systolic blood pressure (SBP) at 12 weeks** [sbpavg], and analyses will compare this change across arms for primary outcome analyses, adjusting for baseline.

Secondary Outcomes

Secondary efficacy outcomes include:

- 1) Mean automated office SBP at 12 weeks, adjusted for baseline values [sbpavg].
- 2) **Other BP measures** that will be compared across arms, controlling for baseline values:
 - a. Mean change (from baseline) in automated office SBP [sbpavg] at six weeks.
 - b. Mean automated office SBP [sbpavg] at six weeks.
 - c. Mean change (from baseline) in automated office DBP [dbpavg] at six and 12 weeks.
 - d. Mean automated office DBP [dbpavg] at six and 12 weeks.
 - e. Proportion of patients with hypertension control (SBP < 130 mmHg and DBP < 80 mmHg) at six and 12 weeks [sbpavg, dbpavg].
 - f. Proportion of patients requiring step-up treatment [amlo_dispnd].
 - g. Proportion of patients with adverse event-free hypertension control (SBP < 130 mmHg and DBP < 80 mmHg [sbpavg, dbpavg]). For the purposes of this outcome, we will define adverse event-free as absence of any events that are documented as either possibly, probably, or definitely related to study medication ([saerelate] = 3, 4, 5).
- 3) **Medication adherence:** proportion of participants deemed adherent to study medication based on the 80% criterion (i.e., participant took at least 80% of assigned study medication). This information will be captured via:
 - a. Objective pill counts [capsret6, lost6, capsret12, lost12], and
 - b. Self-reported measures [forget, miss30, miss7] in addition to the objective pill counts.
- 4) **Health-related quality of life:** Mean change from baseline in health-related quality of life

using PROMIS Global Health instrument [global01—global10]. There are two domains within this construct:

- a. Global Mental Health (assessed via a T-score)
- b. Global Physical Health (assessed via a T-score)

Safety Outcomes

We plan to evaluate the following safety outcomes:

- 1) Proportion of participants with *any* SAE according to the Good Clinical Practice (GCP) definition [sae_present, saedeath, saelifethrt, saehosp, saedisp, saecong, saeimpevnt].
- 2) Proportion of participants with *any* potentially relevant side effect ([sae_term] refer to the adverse event case report form and the list of relevant side effects from the informed consent form).
- 3) Rate of relevant side effects at the participant level (i.e., count per participant [sae_term]).
- 4) Mean change (from baseline) in continuous serum potassium (mEq/L), controlling for baseline value [potassium].
- 5) Mean change (from baseline) in continuous serum sodium (mEq/L), controlling for baseline value [sodium].
- 6) Mean change (from baseline) in continuous blood urea nitrogen (mg/dl), controlling for baseline value [urea].
- 7) Mean change (from baseline) in continuous serum creatinine (mg/dl), controlling for baseline value [creat].

Exploratory Outcomes

The following outcomes are relevant to the overall aims; however, they carry less weight, and we consider them exploratory in nature. This SAP will not focus in detail on analyses of these outcomes, but we anticipate the general analytic approach to apply. In the event of small numbers that would make modeling infeasible, these data may be reported as descriptive statistics.

ABPM measures

24-hour ambulatory blood pressure monitor (ABPM) measures at 12 weeks adjusted for baseline values:

- 1) Mean 24-hour SBP and DBP [overall_abpsbp, overall_abpdpb].
- 2) Mean daytime (0600 to 2200) [awake_abpsbp, awake_abpdpb] SBP and DBP.
- 3) Mean nighttime (2200 to 0600) SBP and DBP [asleep_abpsbp, asleep_abpdpb].
- 4) Proportion of dippers [sys_dip, dia_dip], defined as nighttime BP falling more than 10% from the daytime values OR night / day blood pressure ratio less than 0.9 and greater than 0.8 with normal diurnal blood pressure pattern.
- 5) Mean daytime SBP and DBP load. Load is defined as the percentage of abnormally elevated readings; daytime SBP / DBP elevated readings would be 130 / 80 mmHg or above.
- 6) Mean nighttime SBP and DBP load. Abnormally elevated readings for nighttime SBP / DBP would be 120 / 70 mmHg or above.
- 7) Percentage of participants with morning surge, calculated as the difference between the mean SBP during the morning hours and nighttime trough SBP. Trough SBP is defined as the mean of three SBP measurements: the lowest nighttime SBP and the measurements immediately preceding and following this measurement.
- 8) Coefficient of variation of SBP and DBP assessed through 24-hour ambulatory blood pressure as defined as the ratio of the 24-hour standard deviation of BP / mean 24-hour value.

- 9) Day-night variability (SDdn), which uses the standard deviation (SD) for daytime measurements and, separately for nighttime measurements, to calculate a weighted mean of these SDs.
- 10) Average real variability (ARV), calculated as the average absolute difference between consecutive readings over the 24-hour ABPM period.

We will assess additional exploratory outcomes as needed to inform individual participant data (IPD) meta-analysis with international QUARTET studies. The details of these IPD analyses are reserved for a separate analytic plan.

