## 9. INCLUSION AND EXCLUSION CRITERIA

### 9.1. Inclusion Criteria:

- Adults ( $\geq 18$  years).
- Spanish or English speaker.
- Previous documentation within the past 24 months of hypertension or high blood pressure (SBP 130-179 mmHg or DBP 80-109 mmHg) from general practitioner, pharmacist or health care professional (e.g., medical assistant, physician or nurse).

And either:

1) Untreated (automated) clinic SBP 140-179 or DBP 90-109 mmHg in the last 12 weeks.

Or

2) Monotherapy with clinic SBP 130-159 or DBP 85-99 mmHg in the last 12 weeks.

A SBP or DBP level higher than these thresholds would lead to ineligibility. However, if an individual were eligible based on an in-range SBP or DBP level (i.e., isolated systolic

hypertension or isolated diastolic hypertension), then a lower corresponding DBP or SBP would not lead to exclusion.

And 1 of the following:

- Treatment naïve
- Currently not on treatment (not take in last 4 weeks)
- Currently taking 1 BP lowering drug (ACE, ARB, CCB, thiazide- or thiazide-like diuretic, BB, MRA, alpha blocker) at any dose

The blood pressure inclusion criteria align more closely with the QUARTET trial. The table shows the range of automated office (clinic) blood pressures for inclusion, as well as a comparison with the QUARTET study in Australia. Safety data from QUARTET (Australia) were published in August 2021. Among 591 participants followed for 12 weeks, there were 7 (3%) SAEs in the intervention group (one each of positional vertigo, shortness of breath, non-cardiac chest pain, tonic clonic seizure, fracture of ankle, cholecystitis, and migraine) and 3 (1%) SAEs in the control group (one each of non-cardiac chest pain, pneumonia, and myocardial infarction). There were 12 (4.0%) treatment withdrawals for any event in the intervention group, versus seven (2.4%) in the control group.

	SBP lower limit, mmHg	SBP upper limit, mmHg	DBP lower limit, mmHg	DBP upper limit, mmHg
Automated office (clinic) measurement within the last 12 weeks, untreated	140	179	90	109
Automated office (clinic) measurement within the last 12 weeks, on monotherapy	130	159	85	99
Research grade blood pressure measurement in QUARTET Australia	No limit	No limit	No limit	No limit
Research grade blood pressure measurement (baseline mean)	115	None	60	None

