plan to conduct both unadjusted (for potential covariates mentioned above) and adjusted analyses. The updated details of these analyses are reserved for the statistical analysis plan. The basic analytic model will be as follows for each outcome (Y) for participant i ($i=1\dots N$) at visit j ($j=1, 2$; corresponding to Week 6 and Week 12):

$$Y_{ij} = \beta_0 + \beta_1 I(LDQT) + B_2(Y_{0i}) + B_3 visit + B_4(visit \times study\ arm) + b_i + e_{ij}$$

Under the assumption that error terms $e_{ij} \sim N(0, \sigma^2)$ is the random error term, $b_i \sim N(0, \sigma_b^2)$ is the participant-level random effect. If visit-by-study arm (B_4) is insignificant at the 5% level, we will remove that term from the model, and subsequently, we will further examine for an overall main effect for visit (B_3). If insignificant, we will also remove that effect from the model and evaluate intervention effect via the primary hypothesis test of interest:

$$H_0: \beta_1 = 0 \text{ vs. } H_1: \beta_1 \neq 0$$

for each outcome. However, if the visit-by-study arm interaction term or the visit term alone is significant, we will plan to evaluate the 12-week contrast via model-estimated least squared means as our primary analyses. All between-arm differences at both six- and 12-week time points will be reported as model-based estimates, corresponding 95% confidence limits, and p-value of the corresponding hypothesis test.

Secondary analyses (i.e., those for the secondary and exploratory outcomes of interest) will utilize data from all time points via (generalized) linear mixed modeling (GLMM) methods with the following specifications: identity, logit, or log link for continuous, binary, or count outcomes, respectively; fixed arm, visit, visit-by-arm interaction, and aforementioned covariates; and random participant effect. For secondary analyses, the model adjusted Wald type III tests for fixed effects will first evaluate significance of a visit-by-arm interaction at the 5% level of significance. If insignificant at the 5% level, then this interaction term will be removed and the model Wald type III test for fixed arm effect will evaluate the overall intervention effect in this longitudinal model at the 5% level.

The table below summarizes the general modeling strategy for each outcome. In each case, we plan to conduct both adjusted and unadjusted analyses. Adjusted analyses will include the aforementioned covariates.

Table: Modeling Strategy by Outcome

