Outcome	Variable Type	Model Link Assumption	Note on Covariates
Primary, secondary / exploratory blood pressure measurements at individual study time points	Continuous (assume normality)	Identity	Same as in primary outcome analyses
Dipping at 12 weeks	Binary / categorical	Logit	Indicator of dipping status at baseline in addition to other covariates as in primary analyses
Hypertension control at individual study time points	Binary / categorical	Logit	Same as in primary outcome analyses, including baseline SBP
Requirement for amlodipine add-on therapy	Binary / categorical	Logit	Same as in primary outcome analyses, including baseline SBP
Adverse event-free hypertension control at each study time point	Binary / categorical	Logit	Same as in primary outcome analyses, including baseline SBP
Medication adherence (at least 80%)	Binary / categorical	Logit	Same as in primary outcome analyses, including baseline SBP
Change in PROMIS Global Health	Continuous (assume normality)	Identity	Same as in primary outcome analyses
Indicator for any SAE	Binary / categorical	Logit	Same as in primary outcome analyses, including baseline SBP
Indicator for any relevant side effect	Binary / categorical	Logit	Same as in primary outcome analyses, including baseline SBP
Rate of relevant side effects	Count (Poisson assumption)	Log	Same as in primary outcome analyses, including baseline SBP
Continuous laboratory measurements (potassium, sodium, urea, creatinine)	Continuous (assume normality)	Identity	Same as in primary outcome analyses

Subgroup Analyses and Heterogeneity of Intervention Effects

An exploratory objective of this study is to assess heterogeneity of treatment effect by the following potential hypothesized moderators: age, sex, and race/ethnicity. To address this, we will analyze primary and secondary blood pressure (12-week SBP, DBP) outcomes via the aforementioned

LMMs; we will add an arm-by-<potential moderator> effect in the original model specified above for each potential moderator of interest. Moderation effects will be explored via model-adjusted type III Wald test for fixed effects at the relaxed 10% level of significance. If significant, then we will examine the intervention effect within each subgroup via a series LMMs: male/female, age category, racial/ethnic category.

Agreement between Outcomes

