7. ANALYTIC DATASET

Analyses will include the (modified) intention-to-treat (mITT) dataset, whereby all those participants with data at any follow-up time point and baseline to contribute to analyses will be included in analyses according to arm to which they were randomized, regardless of adherence to the study protocol. We will conduct a sensitivity analysis on the per protocol dataset (defined as 80% treatment regimen adherence) since precise estimates of intervention effect (if any) on outcomes are important in a phase II study.

Power and sample size considerations allowed for some missing data (20%); however, in the event of large amounts of missing data (i.e., more than 10%), multiple imputation analyses will be explored. We will examine rates of missing data for all variables and determine whether the rates vary by participant characteristics, etc. These summarizations will inform potential biases resulting from missing data. Mixed effects models planned for longitudinal analysis are generally robust for unbalanced data across study time points. Additional sensitivity analyses will explore multiple imputation methods and the global sensitivity analysis to evaluate overall trial robustness [2]. These analyses will again serve as sensitivity analyses to the previously outlined analyses.

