8. POWER AND SAMPLE SIZE CONSIDERATIONS

The initial sample size calculations called for a total of 365 participants to be randomized (1:1 allocation). We anticipated an analytic sample size of 292 based on 365 participants at randomization and a 20% dropout rate by the 12-week follow-up time point. We originally based sample size and power calculations conservatively on an independent two-sample t-test. Based on results of interim analyses (refer to Section 10 for details), we updated our recruitment target to 87 participants (1:1 allocation). The analytic sample size of 77 is anticipated based on 87 participants at randomization.

and a conservatively estimated 12% dropout rate by the 12-week follow-up time point based on 8% dropout rate observed through September 2021.

The initial, conservative plan for primary outcome analyses involving an independent two-sample t-test provided an estimated 80% power to detect a 5 mmHg difference in SBP between the intervention and comparator arms assuming a two-sided 5% level of significance and a 15 mmHg standard deviation in outcome. This estimate is based on a 2017 Cochrane systematic review update evaluating the effects of fixed-dose combination therapy and systematic review on quarter dose combination therapy, and a pilot trial of quarter-dose combination therapy [3]. We assumed baseline SBP has a moderate correlation with follow-up SBP ($r \approx 0.50-0.6$); under this assumption, sample size calculations based on ANCOVA has the potential to allow for over 90% power under the same assumptions for remaining parameters.

At the request of the DSMB, we conducted an interim conditional power analysis, taking into consideration information from both the QUARTET USA trial data as of August 2021 and further the QUARTET (Australia) results.¹⁰ These interim analyses, incorporating information to date, suggested that a recruited sample size of at least 77, and a 12% dropout rate, would provide over 90% conditional power based on a sample of 87 randomized participants.

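### The side-effect rate is modelled as a raw count per participant with no exposure term; if early loss differs by arm, the ratio shifts slightly in favour of the arm that loses more

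*SAP*

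**What the plan says.** SAP Section 2 (Safety Outcomes, item 3) names the outcome "Rate of relevant side effects at the participant level (i.e., count per participant [sae_term"]). It is called a rate, but the definition has no time denominator.

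The modelling table in SAP Section 6 gives the variable type as "Count (Poisson assumption") with a log link. Its covariate note points to the primary-analysis covariates plus baseline SBP. The longitudinal model text in the same section lists "fixed arm, visit, visit-by-arm interaction, and aforementioned covariates; and random participant effect". Protocol Section 16.2 says that for side effects that may recur, "descriptive statistics or GLMMs as specified above will be examined". None of these mentions an offset, and the SAP does not say whether the model has one row per participant or one per visit.

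Three other provisions bear on observation time:

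- **Analysis set.** SAP Section 7 includes "all those participants with data at any follow-up time point and baseline to contribute to analyses".
- **Dropout.** SAP Section 8 uses a "conservatively estimated 12% dropout rate by the 12-week follow-up time point based on 8% dropout rate observed through September 2021", overall and not by arm.
- **Withdrawal.** Under Protocol Section 13, a participant who stops study drug for an adverse event stays on the visit schedule. For someone who withdraws from the study, a close-out visit with the 12-week assessments is attempted.

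**The concern.** A Poisson model without an offset estimates a ratio of mean counts. That equals a ratio of rates only if mean observation time is the same in both arms. Here it may not be. Some participants will leave early, and a close-out visit can bring them into the analysis set with short follow-up: someone who leaves at week 3 has a quarter of the planned 12 weeks. One event in 3 weeks then counts the same as one event in 12.

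If one arm loses more people early, its count falls for a reason unrelated to tolerability. Aim 1 of the SAP hypothesises no increase in side effects with the quadruple combination, and this is one of the two side-effect outcomes that bear on that claim. Where the bias exists, it favours the arm with more loss, which is the wrong direction for a tolerability statement.

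**Working it through.** **The plan's own figure.** SAP Section 8 says: "The analytic sample size of 77 is anticipated based on 87 participants at randomization". Check: 87 × (1 − 0.12) = 76.56, which rounds to 77. The figure reproduces. The plan gives no expected value for the side-effect rate.

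**Inputs.** From the documents: 87 randomised 1:1 (44 and 43), 12 weeks of follow-up, overall dropout 8% observed and 12% planned. Assumed: the split of dropout by arm, the fraction f of the 12 weeks observed in a leaver, and a mean of 0.3, 0.6 or 1.0 events per participant over 12 weeks.

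**Expected count ratio with equal true rates.** One count per participant, constant event rate, dropout dA and dB:

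ratio = [1 − dA(1 − f)] / [1 − dB(1 − f)]

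With leaving times spread evenly, f averages 0.5:

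| Dropout, A v B | Calculation | Count ratio |
|---|---|---|
| 12% v 12% | 0.940 / 0.940 | 1.000 |
| 4.0% v 2.4% | 0.980 / 0.988 | 0.992 |
| 12% v 8% | 0.940 / 0.960 | 0.979 |
| 16% v 8% | 0.920 / 0.960 | 0.958 |
| 24% v 0% (extreme) | 0.880 / 1.000 | 0.880 |

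The 4.0% v 2.4% row borrows the only by-arm figure in the documents, from the Australian trial (Protocol 9.1). Those are treatment withdrawals, not loss to follow-up.

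**Effect of the analysis set at 16% v 8%.** Suppose everyone who leaves before week 6 has no follow-up data and so falls outside mITT. Half the leavers go. Those remaining are 8/92 = 8.7% and 4/96 = 4.2%, observed for between 0.5 and 0.75 of the period.

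- f = 0.5: (1 − 0.0435) / (1 − 0.0208) = 0.977
- f = 0.75: (1 − 0.0217) / (1 − 0.0104) = 0.989

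Close-out visits bring some early leavers back in, so the plausible range for this split runs from 0.989 to 0.958, a bias of about 1–4%.

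**Comparison with random error.** The 95% confidence factor is exp{1.96 × √[1/(44λ) + 1/(43λ)]}, where λ is the mean count:

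- λ = 0.3: 2.15
- λ = 0.6: 1.72
- λ = 1.0: 1.52

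A ratio of 0.958 is a shift by a factor of 1/0.958 = 1.04.

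**Simulation** (44 v 43, equal true rates, f = 0.5, 3,000 runs per setting). Without an offset, two-sided type I error was 3.9% to 5.6% for the 4.0% v 2.4% and 16% v 8% splits. At 24% v 0% it was 5.1% to 9.0%, against 4.1% to 5.1% with the offset. With the offset, the mean estimated ratio was 0.985 to 1.007 throughout. These runs assume a constant event rate, which suits the offset.

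**When the offset itself misleads.** Suppose all side effects occur before week 6, and 16% v 8% leave at week 6. The raw count ratio is exactly 1.00. A single whole-period offset gives (1/0.92) / (1/0.96) = 1.04, a false signal of the same size in the other direction. Separate rows for the two intervals avoid this: exposure before week 6 is equal, and no events fall after it.

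**The case against.** The case for leaving the SAP alone is fair in several respects.

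- Follow-up is fixed at 12 weeks, so mean events per participant is a legitimate quantity, and the SAP defines it openly.
- The visit windows of ±7 days apply equally to both blinded arms and give no directional bias.
- If the counts are entered by visit, as the visit and random-participant terms allow, a missed week-12 visit is a missing row and not a zero.
- The outcome is one of seven safety outcomes, and SAP Section 7 plans to examine missing data.

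All of this limits the size of the problem. It does not remove it. The definition points to one count per participant, the unit of analysis is never stated, and interval lengths would still vary with visit-level rows.

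A reader might infer that the plan will make the less tolerated arm look safer, because people leave when they have side effects. The documents do not support that. Stopping drug for an adverse event does not by itself end event collection (Protocol Section 13), people with no follow-up data are outside mITT, and no dropout by arm is given. Nor does the statement from the Australian trial, "There were 12 (4.0%) treatment withdrawals for any event in the intervention group, versus seven (2.4%) in the control group", establish unequal loss here: it concerns treatment withdrawal in another trial, and even read as loss to follow-up it implies a bias under 1% at f = 0.5.

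**Conclusion.** The point holds as a minor, conditional one. The outcome is labelled a rate, defined as a raw count and modelled with no exposure term. Bias needs early loss to follow-up that differs by arm, and the documents neither show nor exclude this. It is zero with equal dropout and about 1–4% under an assumed 16% v 8% split. It would approach 12% only in an extreme such as 24% v 0% at f = 0.5. For the 16% v 8% split it is small against a confidence factor of 1.5 to 2.15, which itself rests on assumed event rates. The primary analysis and the sample size are unaffected.

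**What to change.** In the SAP Section 6 table row for this outcome, state that side-effect counts are modelled per visit interval (randomisation to week 6, then week 6 to week 12 or close-out). Use log(interval length under observation) as an offset and keep the visit term already specified. Say how events and time are allocated when the week-6 visit is missed. Report person-time by arm and the rate ratio with its 95% confidence interval.

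The cost is a line or two in the SAP. Adverse events are already collected at both follow-up visits. It is assumed, since the documents do not show it, that the dates needed for interval length are recorded.

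There is a small downside. The offset assumes a roughly constant rate within each interval, and it does not in general correct loss that is itself related to side effects. The simple count per participant can therefore be kept as a descriptive summary beside the modelled ratio.
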